### Visit Terminology

Visit	Notation used throughout all TLFs
Screening, Days -21 to Day -5, Visit 1	V1 (Screening)
Randomization/Baseline, Day 0, Visit 2	V2 (Day 0)
Treatment Period 1, Day 1, Visit 3	V3 (Day 1) / *Day 1
Treatment Period 1, Day 13, Visit 4	V4 (Day 13) / *Day 13
Treatment Period 1, Day 14, Visit 5	V5 (Day 14) / *Day 14
Treatment Period 2, Baseline, Day 0, Visit 6	V6 (Day 0)
Treatment Period 2, Day 1, Visit 7	V7 (Day 1) *Day 1
Treatment Period 2, Day 13 (±1 day), Visit 8	V8 (Day 13) / *Day 13
Treatment Period 2, Day 14, Visit 9	V9 (Day 14) / *Day 14
End of Trial, Day 29, Visit 10	V10 EOT
Early Withdrawal	Early Withdrawal #

\*Notation for by-treatment group summaries.

#Listing only. Early Termination assessments to be re-assigned as per Section 6.1 Early Withdrawal Assessments for efficacy tables.

Abbreviations: FU: follow-up

## 10. ANALYSIS POPULATIONS

The following populations are defined for analysis:

- Screened Population: All subjects who sign the informed consent form (ICF).
- Intent-to-treat (ITT) Population: All randomized subjects.
  - The ITT population will be the primary analysis population for efficacy analyses. The subjects in the ITT population will be analyzed by the planned treatment..

- Safety Population: All subjects who receive at least one dose of trial treatment.
  - The safety population will be used for all safety analyses, and subjects will be analyzed by the actual treatment received for the safety population.
- Per protocol (PP) Population: All subjects in the ITT population who do not violate inclusion or exclusion criteria or deviate from the protocol in a way that could influence their efficacy assessment. As this trial has a crossover design, subject inclusion in this set will be considered for all periods.
  - The PP population will be used for sensitivity analyses of the efficacy data.

## 11. STUDY POPULATION

### 11.1 Subject Disposition

Subject disposition information will be summarized for the Screened population by treatment sequence and overall and presented by frequency counts and percentages. Percentages will be based on the number of subjects randomized. The following will be considered for summary:

- The number of subjects screened, enrolled, randomized and completed trial
- The number and percentage of subjects in each analysis population
- The number and percentage of subjects:
  - Completing Treatment Period 1
  - Withdrawing during Treatment Period 1 (with reasons)
  - Entering Treatment Period 2
  - Withdrawing during Treatment Period 2 (with reasons)
  - Completing the study trial

The percentages for the reasons for withdrawal will be calculated relative to the number of subjects who withdrew during each period.

All disposition data, including reasons for exclusion from analysis populations, will be listed for the ITT population.

### 11.2 Protocol Deviations

Major protocol deviations that could potentially affect the efficacy or safety conclusions of the study will be identified before database lock and unblinding of individual subject treatment information.

The data review meeting will make the decision whether a subject is excluded from the PP population. Reasons for exclusion of a subject from the analysis and protocol violations (major or minor) will be listed.

All protocol deviations, including the deviation designation (major or minor), category, and an indication of whether the deviation led to the exclusion of a subject from the PP population, will be presented in a data listing.

### **11.3 Eligibility**

The trial population will be adult subjects with refractory or unexplained chronic cough. Refer to Inclusion and Exclusion criteria in protocol for additional details. A listing of subjects not fulfilling any eligibility criteria will be created.

### **11.4 Demographics, Baseline Characteristics, and History of the Disease**

#### **11.4.1 Demographic Data and Baseline Characteristics**

Demographic and baseline characteristics will be summarized for the ITT population by treatment sequence and overall.

#### **Demographic variables include:**

- Age on Consent Date: Years
- Gender: Male, Female (and child-bearing status)
- Ethnicity: Hispanic or Latino, Not Hispanic or Latino, Not Reported, Unknown
- Race: American Indian or Alaska Native, Asian, Black or African American, Native Hawaiian or Other Pacific Islander, White, Not Reported.

Age will be recalculated in years relative to the informed consent date should it be missing from the eCRF.

#### **Baseline characteristics variables include:**

- Height (cm)
- Weight (kg)
- Body Mass Index (BMI) (kg/m^2)
- Smoking History (Never, Current, Former)
- Smoking Pack Years (Years)
- Spirometry (FEV1, FVC, FEV1/FVC Ratio)
- Number of years with chronic cough
  - Calculated as: Age at consent – Age cough began

Descriptive statistics will be presented for age, height, weight, BMI, and smoking pack years. Frequency counts and percentages will be presented for gender, childbearing potential, ethnicity, race, and smoking history (never, current, or former).

#### 11.4.2 Medical History

The verbatim term of the medical history condition/event will be captured in the eCRF and coded using the Medical Dictionary for Regulatory Activities (MedDRA). The version of MedDRA used will be specified in the final Medical Coding Plan.

A summary table will be prepared by treatment sequence and overall for the Safety population. The summary will show the number and percentage of each system organ class (SOC) and preferred term (PT) ordered by descending subject count in the total column by SOC and PT.

Subjects may have more than 1 condition/event per SOC and PT. At each level of summarization, a subject is counted once if he/she reported 1 or more conditions/events at that level.

All medical history data will be listed.

#### 11.4.3 History of Chronic Cough

Chronic cough history includes age cough began, underlying conditions and procedures related to chronic cough.

Procedures Related to Chronic Cough include:

- None / Not Applicable
- 24 hour esophageal pH monitoring
- Endoscopic or Videofluoroscopic Swallow Evaluation
- Barium esophagram
- Sinus imaging
- HRCT
- Bronchoscopy
- Echocardiogram
- Environmental Assessment
- Other Procedure, Specified

A summary table will be prepared by treatment sequence and overall for the Safety population. The summary will show the number and percentage of subjects reporting each underlying condition and procedure. A subject will be counted for every underlying condition and procedure listed if multiple are selected.

## 11.5 Prior and Concomitant Medications

All prior medications taken for cough or underlying triggers at any time prior to screening will be captured as well as any medication taken 28 days prior to screening and during the study (includes over-the counter and prescription drugs).

Prior and concomitant medication verbatim terms in the eCRF will be mapped to the World Health Organization (WHO) Anatomical Therapeutic Chemical (ATC) classification and preferred names using the WHO Drug Global dictionary, version 01 September 2022.

Partial dates will be imputed. For details on imputation rules, refer to Appendix A: Presentation of Data and Programming Specifications. Imputed dates are only used for the classification of a medication as a prior or concomitant medication; no other calculation, such as durations, will be done.

Prior medications are defined as any medication with an imputed start date before or during screening and an imputed stop date before the date of the first administration of study treatment. Concomitant medications are defined as any medication that was started before screening and with an imputed stop date on or after the start date of study treatment, that are ongoing from screening/baseline, or that are taken on or after the start date of study treatment (imputed start date on or after the first dose of study treatment). If the medication cannot be classified as a prior or concomitant medication, the medication will be considered as concomitant. Prior medications will be summarized by treatment sequence and overall by ATC class and preferred name. Concomitant medications will be summarized for each treatment group by ATC class and preferred name. These summaries will present the number and percentage of subjects using each medication.

Subjects may have more than 1 medication per ATC class and preferred name. At each level of subject summarization, a subject is counted once if he/she reported 1 or more medications at that level. Each summary will be ordered by descending subject count in the total column by ATC level and preferred name. The total column will only be used for ordering.

The following rules will be used to assign a concomitant medication to study treatment:

- A concomitant medication will be assigned to the study treatment received immediately before the medication start date.
- Any concomitant medication reported within the washout period between doses will be attributed to the previous treatment received.
- Medications where the imputed start and stop date information indicate that the medication was taken during both treatment periods, the medication will be assigned to both treatments for analysis.

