## 4. STUDY DESIGN

ADX-629-CC-001 is a Phase 2, multicenter, randomized, double-blind, placebo-controlled, two-period crossover trial to evaluate the safety, tolerability, and efficacy of ADX-629 300 mg administered orally BID for 14 days to approximately 50 adult subjects with refractory or unexplained chronic cough.

Subjects will be screened over a period of up to 3 weeks. Eligible subjects will be randomized to one of two treatment sequences. Subjects in one sequence will receive ADX-629 in Treatment Period 1 and matching-placebo in Treatment Period 2, while subjects in the other sequence will receive the matching placebo in Treatment Period 1 and ADX-629 in Treatment Period 2.

[figure not shown]
Subjects will receive their allocated treatment for 2 weeks within each treatment period. Each subject will have a washout period of 2 weeks  $\pm$  2 days between the two trial periods and will undergo a follow-up assessment approximately 1 to 2 weeks after the last dose of trial treatment. Subjects will be required to attend visits for screening and at the start and end of each treatment period. Each visit will require the subject to attend the clinic or to be visited by research staff on consecutive days. At Screening (Visit 1) and on Days 0 (Visit 2 and Visit 6) and 13 (Visit 4 and Visit 8) of each treatment period, the subject will be fitted with a cough recorder to collect cough count data over a period of 24 hours. The cough recorder will be removed the next day once the 24-hour recording has been completed. The trial will include 5 cough recorder sessions in total.

The trial duration for each subject will be up to 11 weeks as follows: up to 3 weeks for screening, 2 weeks for each treatment period, a 2-week washout between treatment periods, and a 2-week follow-up period.

Should a subject discontinue trial treatment, they will be requested to participate in an early (ET) termination visit as soon as possible after the subject stops taking trial treatment. The subjects should have their follow-up visit 1 to 2 weeks after their last dose of trial treatment; however, if their ET visit is more than 1 week after their last dose, they will not be required to have a follow-up safety assessment.

The follow-up safety assessment will be conducted as an in-clinic visit for follow-up laboratory parameters, vital signs, or electrocardiogram (ECG) parameters.

The trial design is illustrated in Figure 1.

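### SAP 11.5 files a medicine started in washout and continued into Period 2 only under the Period 1 treatment, and gives no treatment to a pre-dose medicine that stops before Period 2

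*SAP*

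**What the plan says.** SAP 11.5 gives three assignment rules.

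1. Start date: "A concomitant medication will be assigned to the study treatment received immediately before the medication start date".
2. Washout: "Any concomitant medication reported within the washout period between doses will be attributed to the previous treatment received".
3. Use in both periods. Where start and stop dates show that "the medication was taken during both treatment periods, the medication will be assigned to both treatments for analysis".

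The assignment feeds one summary: "Concomitant medications will be summarized for each treatment group by ATC class and preferred name". Protocol 10.3 asks for the same table and has no assignment rule of its own.

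The same SAP section decides what counts as concomitant. It includes "any medication that was started before screening and with an imputed stop date on or after the start date of study treatment". A prior medication must have "an imputed stop date before the date of the first administration of study treatment". A background medicine stopped after the first dose is therefore concomitant, not prior.

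SAP 4 sets out the calendar as "2 weeks for each treatment period, a 2-week washout between treatment periods, and a 2-week follow-up period". Washout lies between the treatment periods and is part of neither.

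**The concern.** Rules 1 and 2 closely follow the adverse-event rules in SAP 15.1.2, which assign an event by its onset. That suits an event. A medicine has a duration, and what matters is which study treatment it was taken alongside. Rule 3 allows for duration, but only for medicines used in both treatment periods.

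The by-treatment table is the planned way to see whether other medicines were used equally on ADX-629 and placebo. SAP 12.1.3 itself lists medicines thought to modulate or induce cough. In a crossover of about 50 subjects, a few entries in the wrong column, or in none, can change how such a table reads. The timing also matters. The Period 2 baseline recorder is fitted at Visit 6 (Day 0) and removed at Visit 7 before the first dose (Protocol 5.2.2.3 and 5.2.2.4). A medicine started in washout and still taken in Period 2 will therefore almost always overlap that baseline recording.

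**Working it through.** **Step 1. Apply the rules literally.** Nominal calendar from SAP 4: Period 1 dosing on days 1–14, washout on days 15–28, Period 2 dosing on days 29–42. Rule 2 is read as referring to medicines started in washout.

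| Medicine | SAP rules give | Period(s) in which it was taken |
|---|---|---|
| Start day 20, stop day 35 | Period 1 | Period 2 |
| Start day 20, ongoing at end of trial | Period 1 | Period 2 |
| Start day 18, stop day 24 | Period 1 | neither (washout only) |
| Background, stop day 7 | none | Period 1 |
| Background, stop day 20 | none | Period 1 |
| Start day −3, stop day 5 | none | Period 1 |
| Background, subject withdraws on day 8 | none | Period 1 |
| Background, ongoing throughout | both | both |
| Start day 5, stop day 9 | Period 1 | Period 1 |
| Start day 5, stop day 30 | both | both |
| Start day 33, stop day 36 | Period 2 | Period 2 |

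The last four cases are right, and the washout-only case is a reasonable convention. Two cases fall in the wrong column and four in no column.

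**Step 2. Why rule 3 does not help.** A washout start was not taken in Treatment Period 1. A background medicine stopped in Period 1 or washout was not taken in Treatment Period 2. Neither meets the both-periods condition. SAP 11.5 also has a fallback for medicines that cannot be classified, but it settles prior versus concomitant status and not treatment.

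**Step 3. Illustrative size of the first case.** The plan states no figure to reproduce. Assume that start days are uniform over days 15–42, that each course lasts d consecutive days, and that all Period 2 starts are filed correctly.

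- A course starting on day s ends on day s + d − 1. It begins in washout and reaches Period 2 if 30 − d ≤ s ≤ 28, which gives d − 1 start days (for d up to 15).
- Period 2 itself offers 14 start days.
- Share of new medicines taken in Period 2 that are filed only under the other treatment = (d − 1)/(14 + d − 1) = (d − 1)/(13 + d).

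| d (days) | Share |
|---|---|
| 5 | 4/18 = 22% |
| 7 | 6/20 = 30% |
| 10 | 9/23 = 39% |
| 14 | 13/27 = 48% |

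The denominator is narrow. Adding 14 possible start days in Period 1 gives (d − 1)/(27 + d): 4/32 = 12.5%, 6/34 = 18%, 9/37 = 24% and 13/41 = 32%. Counting background medicines as well would lower it further.

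**Step 4. Overlap with the end-of-period recording.** Visit 8 is Period 2 Day 13, calendar day 41. A course started on the last washout day ends on day 28 + d − 1: day 32, 34, 37 or 41 for d = 5, 7, 10 or 14. Of these lengths, only the 14-day course can reach that recording.

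**The case against.** Several points against the concern have weight.

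- **Rule 3 uses stop dates as well as start dates.** It was written for medicines and puts a long-term background medicine taken throughout under both treatments. This stands: the rules are not start-date rules alone, and they are right for stable background therapy.
- **Filing washout starts under the previous treatment matches the adverse-event rule.** A medicine given for a washout event then sits in the same column as the event. This is a fair reason to keep the Period 1 entry. It is no reason to leave out the Period 2 entry when use continued.
- **No rule excludes the unassigned medicines.** They are concomitant by definition and must be tabulated by treatment, so a programmer might place them under Period 1 by default. This stands in part: the gap is an unstated default. It is also limited to starts known to precede first dose, because SAP Appendix A sets a completely missing start date to the first-dose date when the stop date is later or missing. If rule 2 were read to cover any medicine reported as in use during washout, a background medicine stopped there would go to Period 1. One stopped within Period 1 would still have no rule.
- **The table is descriptive.** The models in SAP 12.1.1 do not use the assignment, and SAP 8 provides listings by subject. This stands.

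A reader might infer that the rules hide a real imbalance in cough medicines, or bias the efficacy result. The documents support neither. Misfiling runs both ways, from placebo to ADX-629 in sequence S1 and the reverse in S2, so it would tend to dilute a difference rather than create one. The contents of the prohibited-medication table in Protocol 7.9.1 are not visible, so it is not known which short-course cough medicines were allowed.

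**Conclusion.** The point holds for the by-treatment concomitant medication table. The washout case is a stated rule that gives a wrong count. The pre-dose case is a missing rule, limited to medicines with a start date known to precede first dose. Medicines taken in both periods, and medicines started and stopped within one period, are handled correctly.

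The 22% to 48% range is an illustration, not a forecast. It rests on uniform start days, 14-day washout and treatment periods, and a denominator of new medicines taken in Period 2. The documents contain no data on when medicines were started. Nothing here touches the efficacy estimates or the subject listings. The reason to act is that the correction is cheap and the table would otherwise show some medicines under a treatment they did not accompany.

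**What to change.** Replace the three rules in SAP 11.5 with an overlap rule.

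- Assign each concomitant medication to every treatment whose dosing window (first to last dose of that period) overlaps the medicine's start-stop interval, after date imputation. Pre-dose starts still taken on or after first dose then count under Period 1, and also under Period 2 if use continues.
- Use the previous treatment alone only for medicines that start and stop within washout, or that start in follow-up after treatment.
- If alignment with the adverse-event washout rule is wanted, keep the Period 1 entry for a washout start that continues into Period 2, but also count it under the Period 2 treatment.
- Amend the sentence in SAP 11.5 that restricts imputed dates to prior versus concomitant classification. The third rule already uses them to assign treatment ("Medications where the imputed start and stop date information indicate that the medication was taken during both treatment periods"), and the overlap rule would too.

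The cost is SAP wording and a short change to the dataset derivation, with no new data. Cases that the present rules handle correctly do not change. The downside is that some medicines are counted under one more treatment than before. This includes medicines with a missing stop date, which Appendix A extends to the last known date on study.

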## 12. EFFICACY ANALYSES AND METHODS

The key secondary and secondary efficacy analyses will be based on the ITT population and repeated for the PP population, where indicated, and summarized by treatment group.

The efficacy variables for this trial are:

- Awake cough frequency (average coughs per hour during awake period) measured via the [REDACTED] cough monitor.
- 24-hour cough frequency (average coughs per hour during a 24-hour period) measured via the [REDACTED] cough monitor.
- Cough severity scores (0 – 100) using a visual analogue scale.
- LCQ scores
- CQLQ scores
- Global Rating of Change scores for cough severity
- Global Rating of Change scores for cough frequency
- PGIC scores measured via a rating scale completed by subjects to assess the subject's response to the trial treatment. It consists of a 7point scale ranging from 'very much improved' to "very much worse."
- CGIC scores measured via a rating scale completed by Investigators to assess the subject's response to the trial treatment. It consists of a 7point scale ranging from 'very much improved' to 'very much worse.'

### 12.1 Cough Frequency

#### 12.1.1 Awake Cough Frequency

The key secondary efficacy endpoint is change from baseline in awake cough frequency (total cough count during awake period /duration of awake period [hour]).

Cough frequency will be assessed using the [REDACTED] cough monitor, a 510k approved device that has been successfully implemented in previous clinical trials. The [REDACTED] cough monitor is a digital recording device that uses 2 input channels, biometric sensor and air microphone, to obtain objective cough counts. The first records sounds from the lungs and trachea through a chest contact biometric sensor and the second channel captures ambient sounds through a lapel air microphone.

Subjects will wear the cough monitor for a 24-hour period at Visit 1 (Screening), Visit 2 (Baseline - Period 1), Visit 4 (End of Period 1), Visit 6 (Baseline - Period 2), and Visit 8 (End of Period 2). The average awake cough count (per hour) will be calculated using the total number of coughs during the awake period divided by the duration of awake period (coughs / hour).

Change in Awake Cough Frequency from Baseline = Awake Cough Frequency at the End of Period - Awake Cough Frequency at Baseline, hence a negative result indicates an improvement or decrease in cough frequency, while a positive result indicates an increase. Due to the skewed nature of cough frequency data, awake cough frequency will be log transformed prior to analysis.

The null ( $H_0$ ) and alternative ( $H_1$ ) hypotheses for the key secondary efficacy endpoint (awake cough frequency) can be expressed as:

$H_0$ : The geometric mean cough frequency is equal between ADX-629 and placebo.

$H_1$ : The geometric mean cough frequency is different between ADX-629 and placebo.

A mixed-effect model suitable for the crossover design will be used to make comparisons between the two treatment groups in the changes from baseline of the natural log data. Alternative sensitivity analyses may be performed assessing the impact of any missing data on the interpretation of the results.

Although summaries will be presented for cough frequencies, a log transformation will be used prior to statistical analyses because of the skewed nature of the data. The cough frequency counts will be log transformed prior to calculation of the change from baseline value for each subject. The resulting changes from baseline on the natural log scale will be used as dependant value in statistical testing. All statistical testing will be at the 5% level of significance (2-sided), and 2-sided 95% confidence intervals will accompany all point estimates for the comparison between treatment groups.

A mixed-effect model suitable for the crossover design will be used to compare the two treatment groups' change from baseline in cough frequency on the log scale. The model will include fixed effects for treatment sequence [S1, S2], period [Period 1, Period 2], treatment [ADX-629, placebo] and correlated errors due to treatment. The period-specific baseline values will be included as a covariate.

If there are zero cough frequencies within the data, all values will have 0.1 added to their cough frequency (equating to 1 cough every 10 hours) prior to transforming the data.

The least-squares mean (LSM) change from baseline on the log scale will be presented for each treatment group and the difference between treatment groups.

Estimates from the mixed-effect model will be back-transformed to estimate the ratio comparison to baseline for each treatment group, and the difference between treatment groups will be back-transformed to estimate the ratio comparison to baseline for the ADX-629 group adjusted for placebo. All ratios will be accompanied by the corresponding 95% confidence interval (CI) and p-value.

All model assumptions will be checked by evaluating model residuals. Should the evaluation of residuals indicate a problem with the model assumptions, an alternative analysis will be performed by analyzing the count data on the original scale (observed counts) where the point estimate and confidence interval of the Hodges-Lehmann's median difference for paired groups will be used.

The analysis will also be performed for subgroups based on baseline awake cough frequency median, tercile and quartile classifications as follows:

- Median (< Median/ >= Median)
- Tercile (< Tercile 1/ >= Tercile 1, < Tercile 2/ >= Tercile 2)
- Quartile (< Quartile 1/ >= Quartile 1, < Quartile 2/ >= Quartile 2, < Quartile 3/ >= Quartile 3)

[figure not shown]

Baseline for the above classifications will be the average of the pre-dose values in period 1 and period 2 for each subject.

The key secondary efficacy analysis of awake cough frequency will be repeated for the PP population.

Additionally, the number and percentage of subjects with  $\geq 30\%$ ,  $\geq 50\%$  and  $\geq 70\%$  reduction from baseline, at Day 14, will also be presented by treatment group.

Subjects will be classified as a responder/non-responder for each category ( $\geq 30\%$ ,  $\geq 50\%$  and  $\geq 70\%$  reduction) and treatment groups will be compared using a generalized estimating equation (GEE) for logistic regression with an exchangeable working correlation structure. The model will include fixed effects for treatment sequence [S1, S2], period [Period 1, Period 2] and treatment [ADX-629, placebo]. The period-specific baseline values will be included as a covariate. The odds ratio between ADX-629 and placebo, 95% confidence intervals for the odds ratio, and P-value for the covariate-adjusted treatment comparison will be presented.

Should the GEE model not converge, the model may be adjusted by removing factors or changing the correlation structure. If the GEE is found to be not appropriate for the data a Fisher's exact test will be used to calculate the odds ratio. The final model will be specified in the footnotes of the appropriate tables.

